**The baseline and outcome sessions will take approximately 2 hours each.**

## Section 4 - PARTICIPANT POPULATION

4a. What is the total number of participants (or number of participant records, specimens, etc.) for whom you are seeking Kent State IRB approval?

*The number of participants is defined as the number of individuals who agree to participate (i.e., those who provide consent or whose records are accessed, etc.) even if all do not prove eligible or complete the study. The total number of research participants may be increased only with prior IRB approval.*

64 participants

4b. Explain how this number was derived (e.g., statistical rationale, attrition rate, etc.).

Sample size was determined by conducting a power analysis for power = 0.80 at  $\alpha = .05$  [16] using G\*Power version 3.1 software [17]. In order to ensure that all main hypotheses are adequately powered we utilized the smallest effect size ( $f=.13$ ) indicated among our primary outcomes to calculate the required sample within a repeated measures, between-within factor framework, with two groups and two repetitions. This analysis resulted in an estimated sample size of  $n=64$ , actual power = .811.

4c. Specify the age(s) of the individuals who may participate in the research:

Age(s): **21-65**

4d. Specify the participant population(s) to be included (check all that apply):

 Adults	 Pregnant women/fetuses  Complete Appendix K (Only if pregnant women are intentionally recruited and/or studied)
 Adults with decisional impairment  Complete Appendix W	 Prisoners  Complete Appendix L
 Children (< 18 years)  Complete Appendix I . Research involving minors must adhere to University policy 5-19 .	 Student research pools (e.g., psychology, sociology, communication)  Complete Appendix Y
 Neonates (uncertain viability/nonviable)  Complete Appendix K	 Unknown (e.g., research using secondary data/specimens, non-targeted surveys)
 Non-English speaking  Complete Appendix J	 Other Specify:

*The regulations require that, "When some or all of the subjects are likely to be vulnerable to coercion or undue influence, such as children, prisoners, pregnant women, mentally disabled persons, or economically or educationally disadvantaged persons, additional safeguards have been included in the study to protect the rights and welfare of these subjects." 45 CFR 46.111(b). There are additional, explicit regulatory requirements regarding pregnant women and fetuses (45 CFR 46 Subpart B), prisoners (45 CFR 46 Subpart C) and children (45 CFR 46 Subpart D and 21 CFR 50 Subpart D. The questions in the applicable appendices address these additional requirements.*

4e. Describe the characteristics of the proposed participants, and explain how the nature of the research requires/justifies their inclusion.

Participants will include individuals age 21 years or older endorsing at least three negative consequence of alcohol use in the past month, additional exclusion / inclusion described previously, but who are not interested in seeking treatment from a health care professional. It is necessary to include only individuals age 21 or older to comply with state and federal law regarding alcohol use. It is necessary to include individuals

who endorse at least one negative consequence of alcohol use as those not experience even mild problems related to alcohol use would not be likely to have an interest in using the proposed applications. It is necessary to exclude those seeking treatment as the conditions proposed in the current study have no demonstration of efficacy.

---

4f. Will any participants be excluded based on age, gender, race/ethnicity, medical conditions, pregnancy status, language, education, or financial status?  Yes  No

If Yes  Explain the criteria and reason(s) for each exclusion. Explain who will evaluate and make determinations about subjects that should be excluded from the study. *Consider the study's scientific or scholarly aims and risks.*

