### Section 9 - RESEARCH PROGRESS

A. Summarize the progress of the research, including any interim findings.

**To date, we have consented 34 participants. Recruitment was significantly slowed due to COVID-19 study suspensions and time needed to ensure study procedures conformed to research activity requirements introduced due to the COVID-19 pandemic.**

B. For multi-site studies, summarize the overall progress of the research. *Attach a copy of the most recent multi-site study report, if any.*

N/A

C. Summarize any IRB-approved amendments or changes made to the research since last IRB review (initial or continuing). If IRB approval was not obtained for changes, provide an explanation.

N/A

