Participants will be recruited using the Kent State University SONA system and from the community via flyers and online advertisement. Eligible participants will meet the following inclusion criteria 1) be age 21 or older, 2) report experiencing at least three negative consequence of alcohol use in the past month (assessed via Brief Young Adult Alcohol Consequences Questionnaire: BYAACQ), 3) report having consumed at least 5 drinks (for men) or 4 drinks (for women) on one or more occasions in the past 2-weeks 4) not be seeking treatment for alcohol use from a health-care provider, and 5) have access to a smartphone and 6) endorse some importance in changing their drinking (2 or greater on Alcohol Ladder Scale importance to change). Participants who endorse seeking treatment for alcohol related problems from a health care provider will be provided with a list of university sponsored and community based treatment providers.

Participants (n=64) will complete a battery of assessments detailed below including (1) demographic measures, (2) alcohol and substance use measures, (3) psychological measures, (4) behavioral economic and (5) neuropsychological measures.

**(1) Demographic Measures:** will include brief questions about demographic characteristics biological sex, race, and socio-economic status.

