**Avoid "triggers."** What triggers your urge to drink? If certain people or places make you drink even when you don't want to, try to avoid them. If certain activities, times of day, or feelings trigger the urge, plan something else to do instead of drinking. If drinking at home is a problem, keep little or no alcohol there.

**Plan to handle urges.** When you cannot avoid a trigger and an urge hits, consider these options: Remind yourself of your reasons for changing (it can help to carry them in writing or store them in an electronic message you can access easily). Or talk things through with someone you trust. Or get involved with a healthy, distracting activity, such as physical exercise or a hobby that doesn't involve drinking. Or, instead of fighting the feeling, accept it and ride it out without giving in, knowing that it will soon crest like a wave and pass. Also, see the short module to help you handle urges to drink.

**Know your "no."** You're likely to be offered a drink at times when you don't want one. Have a polite, convincing "no, thanks" ready. The faster you can say no to these offers, the less likely you are to give in. If you hesitate, it allows you time to think of excuses to go along. Also, see the short module to help you build drink refusal skills.

Following the two week observation period participants will repeat baseline assessment procedures including: (2) alcohol and substance use measures, (3) psychological measures, (4) Behavioral Economic and (5) neuropsychological measures. Additionally, participants will complete questionnaires assessing their experience while using 1) the moderation strategies detailed above and 2) [for participants using the mobile application] specific questions regarding use of the application (e.g. The mobile application was easy to use; I would use this mobile application to help monitor my alcohol use). The follow-up measures will be administered via email and collected through Qualtrics online survey platform.

---

3f. Check all research activities that apply. *Attach a copy of materials to be used (e.g., interview/focus group questions, instruments, data collection forms, etc.).*

 Anesthesia (general or local) or sedation	 Magnetic Resonance Imaging (MRI)
 Audio, video, digital, or image recordings	 Materials that may be considered sensitive, offensive, threatening, or degrading

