**Participant will provide consent.**

8e. Check all that apply:

 Informed Consent– Signed Form  Provide copies of document. Please use website template	 Parental Permission – Form
 Informed Consent – Verbal	 Parental Permission – Verbal
 Script/Online/Unsigned form  Provide copies of script/document	 Script/Online/Unsigned
 Assent – Form	 Translated Consent/Assent – Form(s), Script(s), etc.
 Assent – Verbal/Online/Unsigned	 ( provide copy of English version with description the qualifications of the translator. )
 Not Applicable (existing data or specimens)	 Photograph/video/audio taping consent form (or permission for photographs/video/audiotaping included as section on informed consent)
	 Other (Specify):

8f. Describe the consent process. Explain when and where (e.g., in a private room, in a group setting) consent will be obtained and how subjects and/or their legally authorized representatives will be provided sufficient opportunity (e.g., waiting period, if any) to consider participation. *If the person consenting subjects into the study has what could be perceived as a supervisory role (professor, teacher, doctor, counselor, etc...) in the eyes of the subjects, explain how risks will be minimized for participants to feel obligated to participate in the research.*

**Consent will be performed at the beginning of the laboratory session in a private room. All study procedures will be explained to the participant and the research team member obtaining consent will answer any questions posed by the potential participant. Following this, participants will be given an indefinite period of time to review the consent and consider participation in the study.**

8g. Will any other tools (e.g., quizzes, visual aids, information sheets) be used during the consent process to assist participant comprehension?  Yes  [Provide copies of these tools](#)  No

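### The 64 participants needed for the stated power of .811 are also the ceiling on all who consent, with no allowance for loss, so power drops below .80 at the second loss

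*Protocol*

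**What the plan says.** The sample size is justified in the application part of the protocol, Section 4. Item 4b opens "Sample size was determined by conducting a power analysis for power = 0.80 at" alpha .05. It takes the smallest effect size among the primary outcomes, f=.13, within a "repeated measures, between-within factor framework, with two groups and two repetitions", and reports n=64 with actual power .811. The stated purpose of choosing the smallest effect is "In order to ensure that all main hypotheses are adequately powered".

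Item 4a, directly above, requests approval for 64 participants. Its definition counts everyone who consents, "even if all do not prove eligible or complete the study", and the total may rise only with prior IRB approval. Section 10 of the continuing review form repeats 64 as the approved number under the same definition.

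Three other places show where a consented participant can drop out of the analysis:

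- Item 3e applies the same number to the baseline stage: "Participants (n=64) will complete a battery of assessments detailed below".
- Item 8f places consent before any assessment: "Consent will be performed at the beginning of the laboratory session in a private room".
- Item 3e describes the second measurement, after the two-week observation period: "The follow-up measures will be administered via email and collected through Qualtrics online survey platform".

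The prompt to item 4b names attrition as one thing the explanation might cover. The answer does not mention it.

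**The concern.** One figure does two jobs that agree only if nobody is lost. In 4b, 64 is the number that must be analysed: a group-by-time test on two repetitions uses participants with both measurements. In 4a, 64 is the most that may consent. Consent comes before baseline and randomisation, so anyone who then proves ineligible, withdraws or leaves the emailed survey undone uses up one of the 64 and is not replaced under the approved number.

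The .811 is thus the best case, but 4b reports it as the power of the study. The margin over the .80 target is also very thin, so ordinary loss is enough to take the study below its own target for the hypotheses on which it was sized.

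**Working it through.** **Inputs from the protocol (item 4b):** f = .13; alpha = .05; two groups (k=2); two repetitions (m=2); N = 64; stated power .811; target .80.

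**Inputs not given:** the correlation rho between the two repetitions, the allocation ratio (1:1 assumed) and the loss rate (a range is shown).

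**Formula.** For the within-between interaction in a repeated-measures design:

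- lambda = f² × N × m / (1 − rho)
- df1 = (k − 1)(m − 1) = 1
- df2 = (N − k)(m − 1) = N − 2
- power = P(F′ > F critical at .05), with F′ noncentral F(df1, df2, lambda)

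**Step 1: the protocol's own figure.** It cannot be reproduced from the stated inputs alone, because rho is missing. At N=64, rho = .50 gives .535, rho = .70 gives .753, rho = .74 gives .810 and rho = .75 gives .825. Solving for exactly .811 gives rho = .7404. Then lambda = .0169 × 64 × 2 / (1 − .7404) = 2.1632 / .2596 = 8.33, with df 1 and 62. At rho = .74, 64 is also the smallest even N that reaches .80, which fits the protocol's choice. The between-groups main effect does not explain the figure: its power at N=64 is at most .305 for rho from 0 to .9.

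**Step 2: remove participants, holding rho at .7404.**

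| Analysed | Lost of 64 | Power |
|---|---|---|
| 64 | 0 | .811 |
| 63 | 1 (1.6%) | .805 |
| 62 | 2 (3.1%) | .798 |
| 61 | 3 (4.7%) | .792 |
| 58 | 6 (9.4%) | .771 |
| 54 | 10 (15.6%) | .740 |
| 51 | 13 (20.3%) | .714 |

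The smallest N with power of at least .80 is 63.

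**Step 3: does rounding matter?** If .811 is rounded from anywhere between .8105 and .8115, power is .8042 to .8052 at N=63 and .7977 to .7988 at N=62. If f lies between .125 and .1349 and rho is re-solved each time, N=62 still gives .798. The crossing stays at the second loss.

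**Side calculation.** The continuing review reports "To date, we have consented 34 participants". If enrolment ended there and all 34 were analysed, power would be .532. That is a matter of accrual, and the point above does not depend on it.

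**The case against.** The case on the other side has several parts.

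- **The quoted phrase states a purpose.** It explains why the smallest effect was chosen and does not claim power after attrition; .811 is correct for n=64 as written. This stands as a reading of the sentence. But 4b attaches .811 to the study that 4a defines, and that study has at most 64 consents.
- **At two losses the shortfall is trivial.** It is 0.2 percentage points. This stands: the crossing shows how thin the margin is and is not itself a serious loss. The material figures (.77 at about 10%, .71 at about 20%) rest on loss rates that the protocol does not give.
- **The correlation is back-solved.** This also stands. It is the value that makes the protocol's figures consistent for this test, so it neither helps nor harms the argument, but .811 cannot be verified without it.
- **The 64 can be raised with IRB approval.** True, but no plan to do so is stated.
- **Exposure is limited.** Follow-up comes after two weeks, the recruitment flyer pays $40 for the final assessment, and an eligibility screen precedes laboratory consent. Item 3c makes efficacy a secondary objective and Section 2 calls the study preliminary. All of this limits the consequence. None of it reconciles 4a with 4b.

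**Conclusion.** The point holds. The number needed for analysis and the limit on consents are the same 64, no loss is allowed for, and .811 is reached only with complete follow-up of every person who consents. Taking .811 at face value, power is below the .80 target from the second loss and lies between about .79 and .71 for assumed losses of about 5% to 20%. These figures rest on the within-between interaction test, 1:1 allocation and the implied correlation of .74. The importance is moderate: actual loss may be small, and the study's main objective, user experience and willingness to use the application, does not depend on this power. It should be corrected because the power stated is more than the design can be expected to deliver.

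**What to change.** Reword item 4b in three respects:

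1. State that .811 applies to 64 participants with both baseline and follow-up, and give the correlation that was assumed.
2. State an expected loss rate with its basis, and report the power at the number then expected to be analysed within 64 consents. With the implied correlation this is about .79 at 5% loss, .77 at 10%, .74 at 15% and .71 at 20%.
3. Limit the adequate-power statement accordingly, and update the figure if final enrolment falls short of 64.

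This is a change of wording. It needs no added enrolment and no change to design or analysis; the only cost is a less favourable stated power. If the team preferred to keep .811, the approved number would have to be 64 / (1 − loss): 68 consents at 5%, 72 at 10%, 76 at 15% or 80 at 20%, with prior IRB approval. With 34 consented at the continuing review, restating the power is the more realistic course.

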
---

3c. List the scientific or scholarly aims of the research study

The main objective of the current study is to obtain information regarding user experience, overall design, and willingness to use the mobile application in a sample of young adults reporting at least one negative consequence of alcohol use in the past month and endorsing some interest in changing drinking behaviors. A secondary objective of the current study is to examine the initial efficacy of the proposed mobile intervention in reducing negative consequences of alcohol use and to examine correlates of any change (e.g. symptoms of anxiety, drinking motives, executive function).

---

3d. Summarize existing knowledge and previous work that support the expectation of obtaining useful results without undue risk to human subjects. ***Use complete sentences (limit 300 words).***

In general, mobile technologies have been shown to be useful in providing treatment information for a wide-range of health related behaviors for which individuals often fail to seek professional help (Cohn, Hunter-Reel, Hagman, & Mitchell, 2011). Systematic reviews suggest that mobile digital interventions can reduce alcohol use in adults (Fowler, Holt, & Joshi, 2016). Preliminary evidence suggests that non treatment-seeking young adults will engage with a mobile text message intervention incorporating self-regulation support features, and that depending on level of engagement users may meet their drinking goals – suggesting promise for mobile based alcohol reduction interventions (Suffoletto, Chung, Muench, Monti, & Clark, 2018). However, questions regarding the mechanisms, reliability, and magnitude of these effects remain unanswered.

---

3e. Identify and describe the interventions and interactions that are to be performed solely for the research study. *Procedures/interventions should listed sequentially and be separated into paragraphs in the space below.*

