**(3-5) Neuropsychological, Behavioral Economic, and Psychological Measures:** Working Memory Performance and Inhibition will be measured using the National Institute of Health Examiner (Executive Abilities) [8]. The Monetary Choice Questionnaire (Delay Discounting) is a behavioral economic measure for assessing state in subjective value of delayed rewards, with greater discounting of value indicative of decreased self-control[9, 10]. Psychological Measures: will include The UPPS-P Impulsive Behavior Scale: a self-report that assesses five subscales that are used to measure distinct dimensions of impulsive behavior[11]. The Difficulties in Emotional Regulation Scale (DERS) will be used to measure the ability to utilize several emotion regulation strategies. The Positive and Negative Affect Scale will be administered to measure changes in affect[12]. Symptoms of depression, anhedonia, and anxiety will be assessed using the Center for Epidemiologic Studies –Depression Scale (CES-D)[13], SHAPS Anhedonia scale[14], and Generalized Anxiety Disorder 7-item (GAD-7)[15].

Following this initial baseline assessment, participants will be randomized to one of two experimental conditions detailed below. If they are randomized to Alcohol Moderation Group 1 they will receive a link to access the Alcohol Moderation software via smartphone, and a brief demonstration on how to utilize the application will be provided by trained research assistants. Participants will be asked to use the application if they consume alcohol at any point during the two-week observation period. Participants will not be encouraged to use alcohol, and will be clearly informed that there will be no penalty for not using the application during a drinking session or not drinking at all during the two-week observation period.

**Alcohol Moderation Group 1:** Alcohol Moderation group 1 will be introduced to alcohol moderation strategies developed by the National Institute on Alcohol Abuse and Alcoholism. In addition to introducing participants to these drinking moderation strategies they will be asked to download and utilize the Social Drinker application, which addresses many of the strategies. A full description is listed below.

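### Item 4b sizes the trial on a change-score comparison; adjusting follow-up for the baseline already collected is at least as efficient in large samples and needs no extra data

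*Protocol*

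**What the plan says.** Item 4b of the Protocol (Section 4, Participant Population) answers how the number of participants was derived. It states: "Sample size was determined by conducting a power analysis for power = 0.80" at alpha .05 in G*Power 3.1. It takes the smallest effect size among the primary outcomes, f = .13, so that the main hypotheses are all covered, and places it "within a repeated measures, between-within factor framework, with two groups and two repetitions". The result is n = 64 with "actual power = .811". Neither the correlation between the two measurements nor any SD is given.

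The timing of measurement is in item 3e. The assessment battery comes first, and then: "Following this initial baseline assessment, participants will be randomized to one of two experimental conditions detailed below". Later in 3e: "Following the two week observation period participants will repeat baseline assessment procedures including: (2) alcohol and substance use measures", together with the psychological, behavioural economic and neuropsychological measures.

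Item 3c sets the status of the efficacy comparison: "A secondary objective of the current study is to examine the initial efficacy of the proposed mobile intervention in reducing negative consequences". The main objective is user experience and willingness to use the application. The protocol names no other between-group test or model and does not mention baseline adjustment.

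**The concern.** With two arms and two time points, the between-within interaction F is the square of the two-sample t on change from baseline. A change score subtracts the whole baseline value (slope fixed at 1). ANCOVA estimates the slope, so in large samples its variance is never higher, and it is lower unless the best slope happens to be 1. Because the baseline is collected before randomisation anyway, choosing the change score gives up precision for nothing in return.

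Precision is scarce here. The stated power is 1.1 points above target. By the definition in item 4a, the 64 counts everyone who agrees to take part, "even if all do not prove eligible or complete the study", so the number analysed is likely to be lower.

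The size of the gain is uncertain. Item 3e requires participants to "report experiencing at least three negative consequence of alcohol use in the past month". Selecting on past-month consequences could narrow the baseline spread, and a follow-up SD larger than the baseline SD reduces ANCOVA's advantage.

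**Working it through.** **Inputs.** From 4b: f = .13, alpha = .05, two groups, two repetitions, N = 64, power .811. Assumed: equal arms, normal outcomes, two-sided test. Not in the protocol: rho, the baseline to follow-up correlation, and k, the ratio of follow-up to baseline SD.

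**1. Reproduce the stated figure.** For the G*Power within-between interaction, lambda = f² × 2 × N / (1 − rho), referred to F(1, N − 2). The numerator is .0169 × 128 = 2.1632. Power .811 at N = 64 requires rho = .740, which gives lambda = 8.33. At N = 62 power is .798, so 64 is the smallest even total reaching 80%. The between-factor test, lambda = 2.1632 / (1 + rho), cannot give the figure: its power is .305 at rho 0 and .219 at rho .5.

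**2. Confirm that this is the change-score test.** With equal SDs of 1, var(change) = 2(1 − rho). For a group difference D in change, lambda = (N/4) × D² / [2(1 − rho)]. Equating this with step 1 gives D = 4f = .52 SD.

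**3. Compare variances.** With baseline SD 1 and follow-up SD k:

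- change score: 1 + k² − 2·rho·k
- ANCOVA: k²(1 − rho²)

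At k = 1 the ratio of ANCOVA to change score is (1 + rho)/2. At rho .74 that is .870, or 13% lower variance.

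**4. Power.** ANCOVA power uses F(1, N − 3), with lambda divided by 1 + t²/(N − 2) and averaged over chance baseline imbalance, t² ~ F(1, N − 2). For k other than 1 the effect is scaled so that change-score power stays at .811 with N = 64.

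At rho .74:

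| k | Variance ratio | ANCOVA power, N = 64 (change score .811) | Smallest even N for 80% with ANCOVA (change score 64) |
|---|---|---|---|
| 0.9 | .767 | .896 | 50 |
| 1.0 | .870 | .855 | 56 |
| 1.1 | .941 | .828 | 60 |
| 1.2 | .981 | .812 | 64 |
| 1.35 | 1.000 | .804 | not tabulated |

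The last row is k = 1/rho, where the best slope is 1. ANCOVA then saves nothing and pays slightly for estimating the slope.

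Other assumed correlations, equal SDs, N = 64:

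| rho | Variance ratio | Change score | ANCOVA |
|---|---|---|---|
| .5 | .750 | .535 | .650 |
| .7 | .850 | .753 | .811 |

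**5. Incomplete follow-up.** Assume about 10% do not complete, leaving 58. At rho .74 the change score has power .771. ANCOVA has .818 at k = 1.0, .788 at 1.1 and .771 at 1.2.

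**6. Simulation.** With 100,000 trials per setting at N = 64, power for change score and ANCOVA was .813 and .896 (k = 0.9), .811 and .857 (1.0), .812 and .829 (1.1), .812 and .813 (1.2), and .812 and .805 (1.35). At N = 58 and k = 1 it was .773 and .819. Type I error at k = 1.2 was .050 for both tests.

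**The case against.** The strongest reply is that nothing in 4b is an error. It explains how a number was reached, it does not fix the final analysis, and the model may be set in an analysis plan not shown here. This stands as a limit on the point: the change-score test is valid, and under equal SDs the 4b figure is conservative for a later ANCOVA. But 4b does name a comparison and rests the power statement on it. A more efficient comparison on the same data is a better method than the one stated, not a missing detail.

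Second, a between-within framework could be fitted as a longitudinal model with a common baseline mean in both arms, which matches ANCOVA in large samples. That is true, but the power in 4b is not computed for such a model.

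Third, the power figure alone does not prove that the interaction was meant: with two groups and two repetitions, the within-person time test has the same noncentrality and degrees of freedom. That is correct, but the time test compares no groups, so it is not a rival reading of the efficacy comparison.

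Fourth, the gain rests on quantities the protocol does not give, and the entry criterion points towards SD ratios above 1, where it shrinks. The calculation also assumes normal outcomes, which a consequences score with an entry floor may not satisfy. This stands, and it is why the result is given as a range. ANCOVA also does not cure a thin sample: at 58 analysed it is below 80% at SD ratios of 1.1 and 1.2, and at rho .5 it reaches only .650 with all 64.

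**Conclusion.** The point holds as a recommended improvement, with medium confidence. At the correlation implied by 4b (.74), ANCOVA changes power at N = 64 from .811 to between .828 and .896 for SD ratios from 1.1 down to 0.9, with .855 at equal SDs. It makes practically no difference at 1.2 and costs under one point at 1.35, the worst case examined. Lower correlations with equal SDs give larger gains.

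These figures assume equal arms, normal outcomes and the effect size in 4b; the correlation is back-solved and the SD ratios are assumed. What is at stake is precision on a secondary objective. There is no bias, and the main usability objective is not affected.

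**What to change.** State in the protocol that each efficacy outcome (a secondary objective) is compared between groups at follow-up with its own baseline value as covariate (ANCOVA). Restate the power in 4b on that model, giving the assumed baseline to follow-up correlation and the baseline and follow-up SDs, and keep N at 64. The possible saving is better held as margin than used to cut the sample, because it depends on the SD ratio and because 64 counts people who consent.

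The cost is one sentence of analysis wording and one re-run power figure. No new data and no additional participants are needed.
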